All patients presenting with trauma requiring emergent laparotomy will be screened for eligibility for the study. Emergent laparotomy is defined as: (1) time in ED \leq 90 minutes and (2) admission to the OR directly from the ED or IR or prehospital transport (bypass ED and straight to OR from LifeFlight or EMS). Patients meeting all inclusion criteria will be enrolled in the study.

Inclusion criteria

- Emergent laparotomy

- Patient has injuries for which surgeon has equipoise to perform a DEF or DCL
- Age ≥ 16 years (age cut-off for admission to adult trauma service at MHH-TMC)

Exclusion criteria:

- Indication for DCL for which there is no surgeon equipoise:
 - Need for gauze packing of liver or retroperitoneum for hemorrhage control
 - Immediate need to go to IR for hemorrhage control
 - Concern for ACS – defined as physically unable to re-approximate fascia or >10 mmHg change in peak airway pressure during fascial closure
 - Hemodynamic instability – defined as persistent hypotension, ongoing transfusion requirement, or continuous vasopressor use
- Indication for DEF for which there is no surgeon equipoise:
 - Negative and non-therapeutic laparotomies
 - Isolated cystorrhaphy
- Prisoners; known pregnancy; patients with burns $> 20\%$ of total body surface area (resuscitation and treatment differs significantly from trauma patients without burns); patient/legally authorized representative opted out of exception from informed consent (opt out bracelet)
- Currently enrolled in another interventional study

Subjects sixteen years of age and older are considered as adult trauma subjects in a large percent of the trauma centers. Sixteen and seventeen year olds are able to drive in most states and are at high risk for motor vehicle accidents resulting in blunt or penetrating injuries. Excluding this age group would significantly decrease the external validity of the proposed project.

Additionally, it is difficult to differentiate a 16 or 17 year old from one who is 21 or older at the time care is initiated in the ED until positive identification can be obtained. Children below the age of 15 or 50 kg body weight will be excluded from this trial. Children's intravascular volume is different than the adult's, requiring adjustments to the standard adult treatment protocols.

[figure not shown]
Study Procedures

Randomization

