Allocation will occur through sequentially numbered, opaque envelopes kept in the research assistants' office and opened in the operating room. An independent statistician will determine the randomization sequence and oversee the labeling of cards and envelopes. A 1:1 allocation ratio using a permuted block design of 4 or 6 will be used to ensure equal number of patients in each group.

Randomization will occur during the emergent trauma laparotomy. The research assistant will query the attending trauma surgeon periodically throughout the procedure to determine their

Figure 3: Trial randomization flowchart

equipoise between DCL and DEF. If the patient meets all eligibility criteria, that patient will be randomized to DCL (control) or DEF (intervention). The research staff will open the opaque envelope to notify the attending surgeon which group to which the subject has been randomized.

Data Collection

All data will be collected by research assistants utilizing a standardized case report form and entered into a RedCap™ database. Each subject will be assigned a study-specific number. Data will be collected from the clinical pre-hospital emergency medical services run sheets, in hospital records, and the trauma registry. Data will be collected until hospital discharge and questionnaires at discharge and 6 months later.

Data collected will include: demographics, prehospital and injury information, hospital information including ED, OR and post-operative care, discharge information, follow up clinic visits, healthcare cost assessments, and the health status questionnaires completed at discharge and 6 months following injury.

Only laboratory values ordered for and used in standard clinical practice will be collected. No study-specific laboratory tests will be ordered. No biologic specimens will be kept or used.

Follow up

No study-specific follow-up will be required. Six-month questionnaires will be performed by phone call. \$5 Starbucks gift cards will be provided to patients who complete the 6 month follow up questionnaires.

Data and Safety Monitoring

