For DCL patients, adverse events are the primary outcome. Both patients in the DEF and DCL groups are at risk for the same adverse events and the event rate in the proposed groups is unknown. To assess for harm, blinded, univariate outcomes between the two groups will be assessed every 6 months throughout the study period by a data safety and management board (DSMB), which will be organized by CeTIR and headed by [name]. The DSMB will also include an anesthesiologist, a former trauma patient without a medical background who underwent emergent laparotomy, and an independent statistician. At the first meeting following 50% recruitment, a formal Bayesian analysis will be presented to the DSMB to assess the probability of benefit or harm of DCL.

One potential problem area is surgeon adherence to randomization. While the Division of Acute Care Surgery has an excellent record of trauma surgeon buy in for randomized, controlled trials (Early Whole Blood trial, PROPPR, Irricept®), it remains a concern that surgeons will choose not to enroll potentially eligible patients or fail to implement the randomized treatment. To help mitigate surgeon deviation, preliminary work showing indications for which there is equipoise among practicing surgeons has been performed. Additionally, all emergent laparotomies will be evaluated the following day to assess eligibility. If not randomized, the PI will provide real-time surgeon feedback to improve future compliance. Protocol deviations of randomized patients will be documented and reported in publications. Patients will be analyzed on an intent-to-treat basis, so randomized patients will be statistically analyzed in the group to which they were randomized.

Statistics

Sample Size

Over a 2 year period, we aim to enroll 56 patients, 28 in each arm based upon: 1) preliminary data with a MAC rate of 55% in DCL patients and 18% in the DEF patients, 2) alpha=0.05, 3) power=0.80, and 4) dropout rate=10%.

Approximately 55-66 DCLs are performed per year, therefore over 2 years of patient enrollment, enrolling 56 patients meeting eligibility is realistic.

Table 2: Sample size calculations

Enrolled Patients	Expected Difference in MAC (DCL – DEF)
36	47% (65% – 18%)
56	37% (55% – 18%)
108	27% (45% – 18%)

Randomization

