Allocation will occur through sequentially numbered, opaque envelopes kept in the research assistants' office and opened in the operating room. An independent statistician will determine the randomization sequence and oversee the labeling of cards and envelopes. A 1:1 allocation ratio using a permuted block design of 4 or 6 will be used to ensure equal number of patients in each group.

Randomization will occur during the emergent trauma laparotomy. The research assistant will query the attending trauma surgeon periodically throughout the procedure to determine their equipoise between DCL and DEF. If the patient meets all eligibility criteria, that patient will be randomized to DCL (control) or DEF (intervention). The research staff will open the opaque envelope to notify the attending surgeon which group to which the subject has been randomized.

Data Analysis Plan

The number of screened patients and reasons for exclusion will be reported. Protocol violations and reasons for those violations will be reported and detailed. Differences in primary and secondary outcomes across treatment groups will be compared on an intent-to-treat basis using the Wilcoxon rank-sum test, Pearson's Chi-squared, and Fisher's Exact test, for continuous, binary, and sparse binary outcomes, respectively. Exploratory analyses will model outcomes via linear or logistic regression with treatment as the predictor, controlling for any covariates found to be imbalanced across treatment assignment. An independent statistician will provide all data analyses and present them to the DSMB for review.

Given the small sample size of the trial, we will augment the frequentist model described above with a Bayesian analysis to estimate the probability of treatment effects of DCL and DEF.¹⁷

Ethics

This study qualifies for the "Exception from informed consent required for emergency research" (EFIC) as outlined in the FDA regulation 21CFR50.24.¹⁸

1. Subjects are in a life-threatening situation and collection of valid scientific evidence is necessary to determine the safety and effectiveness of the particular interventions
2. Obtaining informed consent is not feasible because the subject cannot give reasonable consent due to medical condition, intervention must be given before consent can be obtained from a LAR, and cannot prospectively select subject

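### The research assistants who ask about equipoise and open the envelopes also keep the unused ones, and the available text describes no seal, opening log or independent reconciliation

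*Combined protocol and SAP*

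**What the plan says.** The combined protocol and SAP gives the procedure twice in the same terms, under Study Procedures (Randomization) and Statistics (Randomization).

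- **Preparation:** "An independent statistician will determine the randomization sequence and oversee the labeling of cards and envelopes".
- **Custody:** "Allocation will occur through sequentially numbered, opaque envelopes kept in the research assistants' office and opened in the operating room".
- **Entry decision:** "The research assistant will query the attending trauma surgeon periodically throughout the procedure to determine their equipoise between DCL and DEF". The matching inclusion criterion is "Patient has injuries for which surgeon has equipoise to perform a DEF or DCL".
- **Reveal:** "The research staff will open the opaque envelope to notify the attending surgeon which group to which the subject has been randomized".
- **Data (Data Collection):** "All data will be collected by research assistants utilizing a standardized case report form and entered into a RedCap™ database".

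Data and Safety Monitoring acknowledges a related worry: "it remains a concern that surgeons will choose not to enroll potentially eligible patients or fail to implement the randomized treatment". Its response includes a review of every emergent laparotomy on the following day, with feedback to the surgeon when a patient was not randomized. The Data Analysis Plan adds reporting of the number screened, the reasons for exclusion, and protocol violations.

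**The concern.** One staff group stores the unused allocations, elicits the statement on which entry depends, reveals the arm and records the data. The independent statistician's described part in allocation ends with the sequence and the labelling.

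Eligibility here is partly a judgement, and the surgeon is asked for it more than once. It can be given or withdrawn until the envelope is opened. If the next arm were known beforehand, that knowledge could affect whether equipoise is declared. Intent-to-treat analysis does not help, because the selection would occur before the patient counts as randomized. Covariate adjustment is planned only as exploratory.

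What is at stake is the comparability of two groups of 28. If higher-risk patients tended to enter when the next arm was DCL, and lower-risk patients when it was DEF, the resulting bias would favor the trial's own hypothesis that DCL does worse.

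**Working it through.** **1. Which steps are described**

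| Step | Described? |
|---|---|
| Independent sequence and labelling | Yes |
| Opaque, sequentially numbered envelopes | Yes |
| Opening in the operating room once eligibility is met | Yes |
| Sealed or tamper-evident envelopes | Not in the available text |
| Patient tied to an envelope before opening | Not in the available text |
| Time of opening recorded | Not in the available text |
| Used and unused envelopes reconciled by someone independent | Not in the available text |
| Next-day review | Yes, for eligibility; envelope order and early opening are not mentioned |

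**2. The plan's own figure.** The plan gives no figure on concealment, so the check uses its sample size. Inputs from Sample Size are 55% v 18%, alpha 0.05 (two-sided assumed), power 0.80 and dropout 10%. With the pooled-variance formula and mean risk (0.55 + 0.18)/2 = 0.365:

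n per arm = [1.96 × √(2 × 0.365 × 0.635) + 0.84 × √(0.55 × 0.45 + 0.18 × 0.82)]² / 0.37² = 25.4.

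25.4 × 1.1 = 27.9, so 28 per arm and 56 in total, as stated. (Rounding up to 26 per arm first and dividing the total of 52 by 0.9 gives 58.) The remedy does not touch this number.

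**3. Illustration of size, with no true treatment effect.** Let m = 36.5% be the mean risk. Half of eligible patients have risk m + s/2 and half m − s/2, where s is the risk spread. In a share q of entries the arm is foreseen and acted on: only high-risk patients then enter DCL, and only low-risk patients enter DEF. Then

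- DCL event rate = m + qs/2
- DEF event rate = m − qs/2
- false difference = q × s

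Example with s = 37 points and q = 0.2: 36.5 + 3.7 = 40.2% v 36.5 − 3.7 = 32.8%, a false difference of 7.4 points.

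Type I error is found by exact enumeration of two binomials at 28 per arm, using the uncorrected Pearson chi-squared test, two-sided at 0.05. With no selection it is 5.0%.

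| Risk spread s | q = 10% | q = 20% | q = 30% |
|---|---|---|---|
| 10 points | 1.0 pt; 5.1% | 2.0 pt; 5.3% | 3.0 pt; 5.7% |
| 20 points | 2.0 pt; 5.3% | 4.0 pt; 6.1% | 6.0 pt; 7.5% |
| 37 points (upper case) | 3.7 pt; 6.0% | 7.4 pt; 8.9% | 11.1 pt; 13.8% |

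If only DEF entries are selected, the 37-point row falls to 5.3%, 6.1% and 7.5%. The error is one-directional: in the 37-point row, false findings that DCL is worse rise from 2.5% to 4.7%, 8.3% and 13.6%.

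Neither q nor s is given in the documents. The 37-point spread borrows the difference between the two planning rates.

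**4. What moving the list would not cure.** The protocol prints the block sizes: "A 1:1 allocation ratio using a permuted block design of 4 or 6 will be used to ensure equal number of patients in each group". With all past arms known and sizes 4 and 6 equally likely (an assumption), the best guess of the next arm is right about 69% of the time, against 50% by chance, without touching an envelope. That is a separate point.

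**The case against.** The case on the other side is substantial, and much of it stands.

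- **Silence is not absence.** The documents do not say whether the envelopes are sealed, and the flowchart (Figure 3) is not shown. It may add steps. The point is therefore limited to what the available text describes.
- **Manipulation would not be invisible.** A reader might infer that an envelope could be passed over without trace. The documents do not support that. A skipped envelope breaks the numbering, staff screen around the clock, each laparotomy is reviewed the next day, and screening, exclusions and violations are reported. What remains is that none of this is described as checking envelope order or early opening, and a statement of no equipoise would by itself account for a non-entry.
- **The evidence on motive concerns surgeons, whereas custody lies with the assistants.** An assistant would have to learn the arm and then act on it or pass it on, and nothing in the documents bears on that. A reader might also infer that the protocol expects surgeons to withhold patients; it voices this only as a concern. The 14-44% range in surgeons' DCL use comes from the earlier quality-improvement project and includes indications now excluded, so it does not show strong preferences among eligible patients.
- **The 37-point spread is extreme.** The two rates are planning figures by arm, not prognostic strata, and the exclusions plausibly narrow the spread. Hence the 10- and 20-point rows.
- **RedCap is described for data collection and entry only.** Its ability to hold a concealed list has to be confirmed. That the assistants know the arm is an inference too, though a sound one, because research staff open the envelope.

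**Conclusion.** The point holds as a design weakness that is cheap to remove. The text puts the future allocations with the staff who elicit the entry decision, entry is subjective, and the described safeguards do not cover envelope order or early opening.

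It does not hold as a finding that concealment failed, that arms were read early, or that the type I error is in fact inflated. A reader might take 13.8% as the expected error; it is the corner of the table with the widest spread and the largest share foreseen. With spreads of 10 to 20 points the inflation is small to moderate, 5.1% to 7.5%. All these figures rest on assumed values of the share foreseen and the risk spread, a 50:50 risk mix and complete two-way selection within the foreseen entries. The case for change rests on the custody arrangement and the low cost of altering it, not on any single cell.

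**What to change.** Revise both Randomization sections as follows.

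1. The independent statistician's list is held concealed from site staff and released one allocation at a time, through the existing RedCap database if its set-up supports this.
2. Before release, the research assistant records the study number, each eligibility item and the surgeon's equipoise statement.
3. Each release is time-stamped and irrevocable, and places the patient in the intent-to-treat set.
4. If this is not available, and in any case as downtime backup, use sealed tamper-evident envelopes. Write the patient number and time on the envelope before opening, log each one, and have the independent statistician reconcile used and unused envelopes before each DSMB report.

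The cost is protocol wording, a one-off set-up, a connected device in the operating room and a short data entry during the operation. Sample size, endpoints and analysis are unchanged. Guessing from the printed block sizes is not addressed by this change and should be handled separately.

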DAMAGE CONTROL LAPAROTOMY: A RANDOMIZED CONTROLLED TRIAL

NCT02706041

Version Date: 06/26/2018

Protocol Title: **DAMAGE CONTROL LAPAROTOMY: A RANDOMIZED CONTROLLED TRIAL**

Principal Investigator: **[name], FACS**
Assistant Professor of Surgery
Faculty, Center for Translational Injury Research (CeTIR)

Co-Investigators: **[name]**
Professor of Surgery
Vice Chair, Department of Surgery
Director, CeTIR

[name], MPH
Professor of Surgery
Faculty, CeTIR

[name]
Professor of Surgery
Deputy Director, CeTIR

Study Coordinator: **[name], R.N.**
Research Project Manager

Population: **Adult trauma patients undergoing emergent laparotomy at Memorial Hermann Hospital-Texas Medical Center (MHH-TMC)**

Number of Sites: **Singe center, MHH-TMC**

Study Duration: **Two years**

Subject Duration: **Time while hospitalized plus 6 months**

Table of Contents

General Information.....	3
Background Information.....	3
Objectives	6
Study Design.....	6
Study Population.....	8
Study Procedures	9
Statistics	9
Ethics.....	10
Data Handling and Record Keeping	10
Quality Control and Assurance.....	10
Publication Plan	10
References.....	11

General Information

This protocol describes a clinical trial comparing damage control laparotomy (DCL) to definitive laparotomy (DEF) in trauma patients undergoing emergent laparotomy. DCL was described in the 1980s and rapidly gained traction over the following decades with increasing rates of utilization and a liberalization in the indications for use. In a DCL, the life-threatening injuries are addressed – bleeding is stopped, enteric spillage is controlled – and the abdomen is left open with a temporary dressing. The patient is then transported to the intensive care unit (ICU) for resuscitation (with the abdomen still open). Once adequately resuscitated, the patient returns to the operating room (OR) for re-exploration of the abdomen, definitive repairs of injuries, and closure of the abdomen. A major hurdle to performing a clinical trial of DCL is surgeon equipoise. There are indications for DCL for which surgeons would not have the clinical equipoise to randomize a patient. Significant preliminary data has identified a group of patients for which there is equipoise to randomize. This proposed trial aims to compare outcomes of patients undergoing DCL versus DEF for which there is surgeon equipoise to randomize.

Background Information

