Beyond these four indications, significant surgeon variation in decision-making exists, indicating equipoise amongst the group. Surgeon equipoise exists for the following indications for DCL: second look (73% potentially unnecessary DCLs), hemodynamic instability with a definition other than continuous vasopressor use or ongoing transfusion (33% potentially unnecessary DCLs), to expedite transfer to CT or the ICU (100% potentially unnecessary DCLs), and to plan an additional wash out of the abdomen due to contamination (100% potentially unnecessary DCLs).

Table 1. QI Project – Nov 2013 – Sept 2015		
Definitive laparotomies	318 (78%)	DCLs deemed unnecessary
Damage control laparotomies	92 (22%)	
Indications for DCL:		
Packing	55 (58%)	4 (7%)
Second look	15 (16%)	11 (73%)
Hemodynamic instability	15 (16%)	5 (33%)
Continuous vasopressors	8	0 (0%)
Ongoing transfusions	6	0 (0%)
Other definition	6	5 (83%)
Expedite CT/ICU	2 (2%)	2 (100%)
Expedite IR	1 (1%)	0 (0%)
ACS prophylaxis	5 (5%)	0 (0%)
Contamination	1 (1%)	1 (100%)

*preliminary data

This variation in the utilization of DCL for specific indications was accompanied by a significant variation in surgeon-specific rates of DCL (Figure 1), which varied from 14-44% and could not be accounted for by the severity of patient injury.

We hypothesize that, among randomized patients, DCL results in increased mortality or major abdominal complications (MAC), defined as an organ/space SSI, enteric suture line failure, fascial dehiscence, or unplanned return to OR after fascial closure for an abdominal complication, within 30 days.

Objectives

To prove or disprove the hypothesis, the specific aims of the proposed project are:

- Aim 1: To perform a single-center, randomized, controlled trial to compare the effect of DCL to DEF on death or MACs within 30 days, additional clinical outcomes, including morbidity, mortality, and lengths of stay.
- Aim 2: To compare resource utilization of DEF and DCL, comparing the direct costs of DCL and the direct costs of the complications associated with DCL and DEF.
- Aim 3: To measure long-term, patient-centered outcomes of the study patients, including health status data, incidence of post-traumatic stress disorder, and return to work.
- Aim 4: To assess feasibility and provide estimates of effect size of individual outcomes for the planning and execute a multicenter, RCT of DCL compared to DEF.

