Primary outcome: death or MAC – a binary, composite variable defined as the development of an organ/space SSI, enteric suture line failure (aka anastomotic leak), fascial dehiscence, or an unplanned return to the OR for an abdominal complication – within 30 days.

Secondary outcomes:

- Non abdominal morbidities – acute kidney failure, adult respiratory distress syndrome, deep vein thrombosis (DVT), pulmonary embolism, pneumonia, and

urinary tract infection, all identified based on standardized definitions used in the National Trauma Databank, to which MHH-TMC already provides patient data.

- Hospital-, ICU-, ventilator-free days – defined as: 30 – total hospital days/ICU days/ventilator days alive = hospital-, ICU-, and ventilator-free days.
- Hospital costs – to be obtained from MHH-TMC
- Patient-centered outcomes – Standard Gamble, EuroQOL-5D(5L), and the Post-Traumatic Stress Disorder Check List-Civilian (PCL-C) to be administered at discharge and 6 months after discharge.

Study Design

This is a single center, RCT involving patients requiring an emergent trauma laparotomy within the first 90 minutes following ED admission due to a severe abdominal injury.

Intervention

Control – DCL

[figure not shown]
Intervention – DEF

Setting

This study will be conducted at the Texas Trauma Institute at Memorial Hermann Hospital-Texas Medical Center (MHH-TMC). It is one of two Level 1 trauma centers in the Houston metropolitan area, an area in which over 6 million people reside, and is the busiest trauma center in the country, with over 6,000 trauma admissions per year. Approximately 220 emergent trauma laparotomies are performed each year, of which 25-35% are DCLs.

Time Period

IRB submission will occur in January 2016, with community consultation beginning shortly thereafter. Eligible patients will be enrolled starting on July 7, 2016. Enrolled subjects will be followed during their post-laparotomy hospitalization and for 6 months following their hospital discharge to assess patient-centered outcomes.

Outcomes

The primary outcome for this study will be a composite variable composed of the following death or major abdominal complications (MAC) within 30 days:

- Deep or organ/space SSI, as defined by the Centers for Disease Control and Prevention¹⁴

- Enteric suture line failure (enteric anastomotic leak) – leakage of enteric contents from gastrointestinal anastomosis

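### The primary outcome runs to day 30, but the data-collection rules conflict after discharge and do not secure day-30 status for every randomized patient

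*Combined protocol and SAP*

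**What the plan says.** **The endpoint.** Objectives, Aim 1 sets out to "compare the effect of DCL to DEF on death or MACs within 30 days". Study Design, Outcomes repeats the window: "The primary outcome for this study will be a composite variable composed of the following death or major abdominal complications (MAC) within 30 days".

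**The data.** Study Procedures, Data Collection names the sources: "Data will be collected from the clinical pre-hospital emergency medical services run sheets, in hospital records, and the trauma registry". The next sentence gives the cut-off: "Data will be collected until hospital discharge and questionnaires at discharge and 6 months later". Data Handling and Record Keeping repeats both sentences. The following paragraph of Data Collection lists the items to be collected, and these include "discharge information, follow up clinic visits, healthcare cost assessments".

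**The follow-up.** The Follow up section says "No study-specific follow-up will be required" and "Six-month questionnaires will be performed by phone call". The title page gives a subject duration of "Time while hospitalized plus 6 months", but Study Design, Time Period gives the months after discharge the purpose of patient-centered outcomes. Study Design, Outcomes describes the 6-month contact as health state, a PTSD checklist and return to work.

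**The analysis.** The Data Analysis Plan specifies intent-to-treat and names the tests. It says nothing about a patient whose day-30 status is not known.

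**The concern.** The endpoint has a fixed 30-day window, while the stated end of clinical data collection is discharge, which comes at a different time for each patient. The plan itself expects some patients to leave before day 30, because hospital-free days are defined as 30 minus days in hospital. Organ/space infection and unplanned return to the operating room after closure are not confined to the first stay. A death after discharge has no stated source: the secondary mortality outcome covers only in-hospital deaths and hospice discharges.

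Three kinds of event are therefore exposed: deaths after discharge, complications treated at another hospital, and complications that the patient does not bring to this center's clinic. If such events are lost equally in both arms and scored as non-events, the observed difference shrinks and power falls. If the loss differs by arm, the comparison is biased. With 56 patients, a few misclassified outcomes matter. Aim 4 uses the effect estimates to plan a multicenter trial, so the error would carry forward.

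**Working it through.** **1. Side by side.**

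| Question | What the plan provides |
|---|---|
| How long is the outcome window? | 30 days (Objectives; Study Design, Outcomes) |
| When does clinical data collection end? | Discharge (Data Collection; Data Handling and Record Keeping) |
| What clinical data come after discharge? | Clinic visits are a listed item, with no timing or attendance requirement |
| Is there a day-30 contact, readmission search or vital-status check? | None described |
| Does the 6-month call ask about death or complications? | Not described |
| How is unknown day-30 status counted? | No rule |

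Capture after discharge is therefore partial, not nil, and nothing makes it complete.

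**2. The plan's own sample size.** Inputs from Statistics, Sample Size: 55% and 18%, alpha 0.05 (two-sided assumed, since the plan does not say), power 0.80, dropout 10%. With pooled rate (0.55 + 0.18)/2 = 0.365:

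n per arm = [1.960 × √(2 × 0.365 × 0.635) + 0.842 × √(0.55 × 0.45 + 0.18 × 0.82)]² / 0.37² = [1.960 × 0.681 + 0.842 × 0.629]² / 0.1369 = 25.4, rounded up to 26.

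Allowing for dropout, 26/0.9 = 28.9, so 29 per arm and 58 in total. That is within two patients of the stated 56. The arithmetic of the sample size is not at issue.

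**3. Equal loss in both arms.** The share missed, m, is an assumption; the documents give none. It is also assumed that 55% and 18% are fully captured 30-day rates of the primary outcome (the plan labels them MAC rates) and that missed events are scored as non-events. Observed rate = true rate × (1 − m). Power is by exact enumeration of two binomials, uncorrected Pearson chi-squared, two-sided 0.05, 28 per arm.

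| m | DCL | DEF | Difference (points) | Power |
|---|---|---|---|---|
| 0% | 55.0% | 18.0% | 37.0 | 0.846 |
| 10% | 49.5% | 16.2% | 33.3 | 0.786 |
| 20% | 44.0% | 14.4% | 29.6 | 0.710 |
| 30% | 38.5% | 12.6% | 25.9 | 0.619 |

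**4. Loss in one arm only.** Take no true difference, with 36.5% in both arms. Missing 10%, 20% or 30% of events in one arm creates a false difference of 0.365 × m, that is 3.65, 7.3 or 10.95 points. At 28 per arm, the two-sided rejection rate rises from 5.0% to 6.1%, 9.2% or 14.7%. Which arm would lose more is not known.

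**5. The counting rule.** Invented data near the planned rates, with three unknown per arm (uncorrected chi-squared):

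| Rule for unknowns | DCL | DEF | p |
|---|---|---|---|
| Excluded | 14/25 | 5/25 | 0.009 |
| All non-events | 14/28 | 5/28 | 0.011 |
| All events | 17/28 | 8/28 | 0.016 |
| Events in DEF only | 14/28 | 8/28 | 0.10 |
| Events in DCL only | 17/28 | 5/28 | 0.001 |

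In this example the three symmetric rules agree. Only the extreme rule that counts unknowns as events in DEF alone changes the conclusion.

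**The case against.** The strongest reply is that the plan does collect data after discharge. Clinic visits are a listed item, and hospital records need not mean the first admission alone, so a readmission or reoperation at this center could fall within them. This stands in part. A reader might infer that nothing is collected between discharge and the 6-month questionnaire, and the documents do not support that. They do support a conflict between the discharge cut-off and the clinic-visit item, with no provision that reaches every patient.

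Second, the power figures take 55% and 18% as complete 30-day rates. The plan calls them preliminary and does not say how, or to what day, they were ascertained. If they came from records with similar gaps, the missed share is already in them and the further loss is smaller or nil. This stands, and it limits the table in step 3 to an illustration. A 10% miss takes power only just below 0.80, and nothing in the documents supports a share of 20% or more.

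Third, a reader might infer that unknowns will be scored as non-events. The plan gives no rule in either direction, so that is a possibility and not a stated intention.

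Fourth, the start of the 30 days is not stated. This is minor: time in the emergency department is at most 90 minutes and randomization occurs during the laparotomy, so admission, operation and randomization normally fall close together.

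The 10% dropout allowance does not answer the point. It is a sample-size margin, not an analysis rule, and it does not cover a discharged patient recorded as event-free.

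**Conclusion.** The point holds as an inconsistency between the endpoint and the stated data collection, and it should be fixed. Followed as written, the rules capture primary events after discharge and before day 30 incompletely, and nothing says how unknown status is handled. That much rests on the text alone.

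The size is not established. Power of 0.79 to 0.62 for 10% to 30% missed depends on assumed shares, equal loss in both arms, scoring as non-events, and planning rates that are themselves complete. A reader might infer that the trial is underpowered, or that the comparison is biased toward one arm. The documents support neither: they give no length of stay by arm, no timing of complications and no share of care at other hospitals. Treatment and sample size need no change on this account.

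**What to change.** 1. In Data Collection and in Data Handling and Record Keeping, move the end of outcome collection from discharge to the later of discharge and day 30 after randomization. This also settles the start point. Reconcile the new wording with the clinic-visit item and with the statement that no study-specific follow-up is needed, and add the primary outcome to the follow-up purpose in Time Period.
2. In both arms and by the same method, have existing research staff review this center's inpatient, readmission, operative and clinic records, and vital status, to day 30. As a supplement, add dated questions to the 6-month call on readmission, abdominal infection, reoperation and death, including care at other hospitals. A family contact should be able to answer, since a patient who has died cannot.
3. Define the primary analysis as patients with confirmed day-30 status plus any patient with an event already recorded. Do not score unknown status as no event. Report unknowns by arm. Show sensitivity analyses in all randomized patients with unknowns all events, all non-events, and opposite by arm. These are needed because the primary rule drops only patients without a recorded event and so can raise the observed rates.

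The cost is wording changes, a case report form page, and record-review time for 56 patients. Recall and non-response limit the call, and some events at other hospitals may stay unconfirmed unless outside records are obtained.
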